## *Background*

Thoracic ultrasound (TUS) differs from ultrasound examinations in other organ systems, because it is not possible in the healthy, ventilated lung to visualize structures or anatomical parts of the lung, like it is when examining abdomen or performing an echocardiography [1,2]. It is therefore not possible to transfer results directly from educational studies using simulation-based training in other areas of medicine, to thoracic ultrasound.

TUS examinations are considered safe, and without pain, exposure to radiation or delay of patients' course, but ultrasound in general is highly operator dependent [1] and lack of theoretical knowledge or practical skills could potentially lead to incorrect diagnosis and thus treatment. Therefore simulation-based training, theoretical and practical tests could be the key to a "pre-trained novice" with a level of competency higher than a complete novice when performing the first TUS examination on a patient in a clinical setting.

The objective of this trial is to examine whether TUS training on a simulator is superior to training on healthy figurants, which today is a commonly used method for gaining skills and competencies in TUS. Secondly, to examine whether the choice of hands-on training has an effect on the number of examinations performed by the trainees from baseline to 4 months follow-up.

## **Methods**

The design is a three-armed, multicentre, blinded randomized controlled trial.

### *Setting*

The trial takes place at three simulation centres at university hospitals in Denmark; Odense University Hospital, Rigshospitalet, and Aarhus University Hospital. The intervention period is scheduled to run from August 2018 to May 2019.

### *Participants*

All physicians employed at public hospitals in Region of Southern Denmark, Capital Region of Denmark, Region Zealand, and Central Denmark Region, are eligible for inclusion in the trial. Because physicians from a wide range of specialities can benefit from TUS examinations, no exclusion criteria are established based on the specialities from the physicians.

The promotion of the educational program and trial is done through posters at the respective departments, social media, and educational groups. Trainees sign up for participation, and inclusion

by mail, and will receive a reply including information about the trial. Exclusion criteria are; lack of informed consent, physicians with connection to the trial, or involvement in the design or conduction.

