#### *Prior to intervention*

Prior to the randomization all participants will complete an online educational programme in TUS in order to reach sufficient theoretical knowledge, and must pass a theoretical test and answer a questionnaire regarding previous experience with ultrasound in general and TUS, current position and employment. All included participants will receive a study identification number that makes it possible to pair the results from the questionnaire to the intervention and performances.

All materials needed prior to the theoretical test, including online educational material, log-in to questionnaire and test will be send to the participants by mail as well. The online educational material comprises access to Munksgaards' online portal in basic ultrasound, which includes theoretical sonographic sessions, instruction videos in TUS, practical hands-on demonstrations, ultrasound clips, and vodcasts. The preparation is estimated to 2-3 hours. The theoretical test is administered in Research Electronic Data Capture (REDCap) provided by Odense Patient data Explorative Network (OPEN). Participants will be excluded if they do not complete the test.

When participants have completed the test, they will move on to part two, which is the practical hands-on training. Part two of the trial will take place in one of the simulation centres. All participants will receive an introduction to the ultrasound machine. A medical student working on the project will do the introduction, which comprises following general information about ultrasound but no information about TUS:

- Turn on/off
- Select and change transducer
- Select preset
- Adjust depth, gain and focus
- Store images/clips

Subsequently, the randomization will take place.

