### *Outcomes*

The primary outcome is difference in LUS-OSAUS score between the three groups [6]. The LUS-OSAUS score is calculated as the sum of all 17 items in the tool (min. 17, max. 85 point), evaluated by instructor and first author, PP. The participant is evaluated two consecutive times.

The LUS-OSAUS tool is, to our knowledge, the first assessment tool with established evidence of validity. The publication shows that LUS-OSAUS can differentiate between different levels of competencies.

Secondary outcome is difference in number of scans performed from baseline to follow-up (4 months) between the two intervention arms.

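### Entry sets no upper limit on prior thoracic ultrasound (TUS) skill, although the rationale and course content are aimed at physicians before their first patient scan

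*Combined protocol and SAP*

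**What the plan says.** Under Participants, the population is wide: "All physicians employed at public hospitals in Region of Southern Denmark, Capital Region of Denmark, Region Zealand, and Central Denmark Region, are eligible". The only exclusions listed there are these: "Exclusion criteria are; lack of informed consent, physicians with connection to the trial, or involvement in the design or conduction". Prior to intervention adds one more: "Participants will be excluded if they do not complete the test". The test sets a minimum of theoretical knowledge; it puts no maximum on skill.

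The same section has participants "answer a questionnaire regarding previous experience with ultrasound in general and TUS, current position and employment", before randomisation, with a study number linking the answers to later performance. No entry rule is attached to the answers. Randomization describes no stratification by experience, and Statistical analyses names training arm as the only independent variable in the ANOVA. Limitations mentions possible stratification, but its examples (machine access, supervision, other courses) act between baseline and follow-up.

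The Background describes the hoped-for product of training as a physician "with a level of competency higher than a complete novice when performing the first TUS examination on a patient in a clinical setting". The content matches that: a basic ultrasound portal taking 2-3 hours, a machine introduction that begins with switching it on, and up to 2.5 hours of practice.

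**The concern.** A physician who already scans lungs routinely is past the point that the rationale describes, yet may be randomised to any arm, including no hands-on training, and enters the primary analysis. It is plausible that such a person gains little from a short beginner session, whichever training arm they are in. Prior skill should also show in the primary outcome, since Outcomes says of the score: "The publication shows that LUS-OSAUS can differentiate between different levels of competencies".

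Three things would follow. The average simulator-figurant difference would be smaller than the difference in novices. Scores would be more spread out within arms. With 22 per arm, and neither stratification nor a covariate for experience, the arms could differ by chance in how many skilled operators they contain. The 4-month scan count could be diluted in the same way if established users keep scanning whatever their arm.

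**Working it through.** **Inputs from Sample size:** difference 8.5 points between the two training arms, SD 8.67, 5% significance (two-sided, per Statistical analyses), power 90%, 22 per group.

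**Assumptions, none of them in the documents:** a share f of entrants is experienced; they gain nothing from either training; they score h points above figurant-trained novices; the 8.5 and 8.67 describe novices.

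**1. The plan's own figure.** n = 2 × [8.67 × (1.960 + 1.282) / 8.5]² = 21.86, rounded up to 22. This reproduces the plan. Power at 22 per arm is 90.2% by the normal approximation and 88.8% by the noncentral t, which is used from here on.

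**2. Diluted difference.** Expected difference = 8.5 × (1 − f): 8.075 at 5%, 7.65 at 10%, 6.80 at 20%.

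**3. Wider spread.** If the experienced are h points above novices in the figurant arm and gain nothing, they are only h − 8.5 above novices in the simulator arm, because those novices have moved up by 8.5. With 8.67² = 75.17:

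- Figurant variance = 75.17 + f(1 − f)h²
- Simulator variance = 75.17 + f(1 − f)(h − 8.5)²
- Pooled SD = square root of the mean of the two

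For f = 10%, h = 20: the variances are 75.17 + 0.09 × 400 = 111.17 and 75.17 + 0.09 × 132.25 = 87.07, so the SD is 9.96. The noncentrality is 7.65 / (9.96 × √(2/22)) = 2.55, and power is 70%.

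| f | difference | power, SD kept at 8.67 | power, h = 0 | power, h = 20 |
|---|---|---|---|---|
| 0 | 8.5 | 89% | – | – |
| 5% | 8.075 | 85% | 85% | 80% |
| 10% | 7.65 | 82% | 80% | 70% |
| 20% | 6.80 | 72% | 69% | 53% |

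Power is nearly flat for h between 0 and 8.5 and falls only beyond that. The column with SD kept at 8.67 is a ceiling. It is also roughly what a covariate that removed all the extra spread could recover, because a covariate does not restore the diluted difference. All figures are before the planned Bonferroni correction, which would lower each of them.

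**4. Excluding without replacing.** At f = 10%, 22 × 0.9 = 19.8, about 20 per arm; with the full 8.5 points and SD 8.67, power is 86%, against at most 82% with the experienced left in. At f = 20%, 22 × 0.8 = 17.6, about 18 per arm; power is 82%, against at most 72%.

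**5. Chance imbalance.** Treat the number of experienced operators in each arm as binomial (22, f). The two training arms then differ by three or more with probability about 20% at f = 10% and 34% at f = 20%. At h = 20, three extra in the figurant arm raise its mean by 3 × 20 / 22 = 2.7 points; three extra in the simulator arm raise its mean by 3 × 11.5 / 22 = 1.6 points. The target difference is 8.5.

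**The case against.** The strongest reply is that the trial never says it is for novices only. Its objective is to "examine whether TUS training on a simulator is superior to training on healthy figurants", and neither the Table 1 hypothesis nor the Discussion restricts this to novices. Open entry may be a deliberate all-comers choice. This stands: the mismatch is between rationale and eligibility, not between objective and eligibility.

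A reader might infer that the trial result would be biased. The documents do not support that. Allocation is random, experience balances in expectation, and the contrast is unbiased for the people enrolled. It falls short only as an estimate of the effect in novices.

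The size is also assumed throughout. Sample size does not say where 8.5 and 8.67 come from; if they already reflect a mixed group, the calculation counts the dilution and spread twice. A 20-point head start is about 2.3 SDs (20 / 8.67), and no section supports it. A reader might also infer that skilled operators have no room to improve under the maximum of 85 points, but the documents report no scores by experience level.

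Finally, the share may be small. Participants volunteer without pay for a basic course and risk allocation to no hands-on training, so a routine lung sonographer has little visible reason to join. That is plausible, but recruitment is open, through posters and social media, and no rule ensures it. If the share is near zero, the exclusion costs almost nothing.

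**Conclusion.** The gap is real and worth closing, as an inexpensive improvement and not as a flaw that invalidates the comparison. No section limits prior TUS skill, and nothing in the randomisation or primary analysis uses the experience that is recorded. The consequence is a smaller average difference than in novices, a wider spread, and exposure to chance imbalance.

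The 80-70% and 69-53% power figures, against 89% as planned, are illustrations. They hold only if experienced operators gain nothing, the planning values describe novices, and the share is 10% or 20%; at 5% the range is 85-80%. The case for the change does not need the lower ends: under the same zero-gain assumption, leaving the experienced out gives more power than keeping them in, even if they are never replaced.

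**What to change.** Add one line to the exclusions under Participants: physicians whose pre-randomisation questionnaire shows that they already perform TUS independently are not randomised, though they may still attend the course. Fix the cut-off that defines this before enrolment starts, and check that the questionnaire has an item from which it can be read.

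If the sponsor prefers entry open to all, say so, and prespecify in Statistical analyses and Table 1 an analysis restricted to novices by the same baseline definition. Experience as a covariate is worth adding in that case, but it addresses spread and chance imbalance only.

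The cost is small, since the questionnaire is already completed before randomisation. A few volunteers would be lost to the randomised comparison, recruitment may be slower, and the result would apply to TUS novices only.

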#### *Prior to intervention*

Prior to the randomization all participants will complete an online educational programme in TUS in order to reach sufficient theoretical knowledge, and must pass a theoretical test and answer a questionnaire regarding previous experience with ultrasound in general and TUS, current position and employment. All included participants will receive a study identification number that makes it possible to pair the results from the questionnaire to the intervention and performances.

All materials needed prior to the theoretical test, including online educational material, log-in to questionnaire and test will be send to the participants by mail as well. The online educational material comprises access to Munksgaards' online portal in basic ultrasound, which includes theoretical sonographic sessions, instruction videos in TUS, practical hands-on demonstrations, ultrasound clips, and vodcasts. The preparation is estimated to 2-3 hours. The theoretical test is administered in Research Electronic Data Capture (REDCap) provided by Odense Patient data Explorative Network (OPEN). Participants will be excluded if they do not complete the test.

When participants have completed the test, they will move on to part two, which is the practical hands-on training. Part two of the trial will take place in one of the simulation centres. All participants will receive an introduction to the ultrasound machine. A medical student working on the project will do the introduction, which comprises following general information about ultrasound but no information about TUS:

- Turn on/off
- Select and change transducer
- Select preset
- Adjust depth, gain and focus
- Store images/clips

Subsequently, the randomization will take place.

### *Randomization*

Randomization is done in REDCap, which allows an online, computer-generated allocation sequence concealed to the project leaders. Participants are randomized for hands-on training on simulator, healthy figurants, or no intervention, last mentioned serve as controls. The ratio for each category is 1:1:1. There is no stratification for site (location).

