### *Sample size*

Significance 5%, Power 90%, mean difference wanted between the two interventional groups is 8.5 point. Standard Deviation 8.67. Sample size per group is 22 (total; 66 participants).

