### *Statistical analyses*

Data will be accessed using OPEN analyse, and analysed using STATA and SPSS. OPEN Analyse is an analyse environment that complies with the current regulations on data privacy. OPEN Analyse acts as terminal server solution from the researcher's private PC with logging if files, but data are stored and processed on a server at the Regional IT.

A two-sided significance level of 0.05 will be used. Statistical methods for the primary and secondary outcomes are presented in Table 1, and include Post Hoc ANOVA with Bonferroni correction, hands-on training facility as independent variable (SIM, FIG, controls), and LUS-OSAUS scores as dependent variable.

All data will be analysed as intention to treat, therefore missing data will be handled by multiple imputation technique, even though missing data are expected to be minimal because instructors are registering a great amount of the data to the database.

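### Site enters neither the randomisation nor the primary ANOVA, so any between-site variance in the LUS-OSAUS score stays in the error term: a loss of precision of unknown size, and cheap to remove

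*Combined protocol and SAP*

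**What the plan says.** The Setting section states: "The trial takes place at three simulation centres at university hospitals in Denmark". Under Randomization the sequence is generated online in REDCap and concealed from the project leaders. "The ratio for each category is 1:1:1", and then "There is no stratification for site (location". No reason is given.

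Under Statistical analyses the model has "hands-on training facility as independent variable (SIM, FIG, controls), and LUS-OSAUS scores as dependent variable". Table 1 likewise lists an ANOVA with Bonferroni correction and names no site factor or covariate. Under Trial intervention, the score is obtained in the emergency department on real patients with suspected thoracic disease; no standard set of cases is described. The Limitations section foresees stratifying for questionnaire items that may influence clinical training during follow-up, such as access to a machine, supervision and courses. Site is not among them.

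**The concern.** Site is known before allocation and is the obvious grouping in a three-centre trial. The patients on whom trainees are scored, and the local setting, can differ between hospitals. If mean scores differ by site, two things follow. The between-site variance is counted as residual error in the ANOVA. And with 22 per arm, the arms can by chance be spread unevenly over the sites, which moves the estimated difference up or down.

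The sample size leaves no slack to absorb this: 22 per group only just reaches the stated power at an unadjusted 5% level. Handling site in the design, the analysis or both would remove this source of noise at little cost.

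**Working it through.** **Inputs from the documents.** Sample size section: "mean difference wanted between the two interventional groups is 8.5 point"; "Standard Deviation 8.67"; power 90%; 22 per group, 66 in total. Statistical analyses: "A two-sided significance level of 0.05 will be used". The plan does not say whether 8.67 is a total or a within-site SD.

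**Assumptions.** The documents give no between-site variance. I take three equal sites with means at -s/2, 0 and +s/2, for spans s of 4 and 8 points. The between-site variance is then 2(s/2)²/3 = s²/6.

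**Step 1: the plan's own figure.** n = 2[(1.960 + 1.282) × 8.67/8.5]² = 21.86, so 22 per group, as stated. Normal-approximation power at 22 is 0.902. The t-test version gives 0.888.

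**Step 2: power with and without a site term, taking 8.67 as the total SD.** The total variance is 8.67² = 75.17.
- s = 4: site variance 16/6 = 2.67, or 3.5% of the total; residual SD √(75.17 - 2.67) = 8.51.
- s = 8: site variance 64/6 = 10.67, or 14.2% of the total; residual SD √(75.17 - 10.67) = 8.03.

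The standard error of the simulator-figurant contrast is SD × √(2/22). Power comes from the noncentral t distribution with noncentrality 8.5/SE, on 63 df for arm only and 61 df with site. The site-term rows assume arms balanced over sites.

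| Analysis | Residual SD | SE | Power at 0.05 | Power at 0.05/3 |
|---|---|---|---|---|
| Planned, arm only | 8.67 | 2.61 | 0.893 | 0.783 |
| Site term, span 4 | 8.51 | 2.57 | 0.903 | 0.799 |
| Site term, span 8 | 8.03 | 2.42 | 0.932 | 0.849 |

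The last column applies the Bonferroni level for three pairwise comparisons. The drop from 0.893 to 0.783 in the first row comes from Bonferroni and has nothing to do with site.

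**Step 3: which part of the remedy does the work.** Simulated power with the 8-point span and equal sites:
- site term, no stratification: 0.927 at 0.05 and 0.831 at 0.05/3;
- site term and stratification: 0.925 and 0.848.

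Stratification adds nothing detectable at 0.05 (the 0.002 is simulation noise) and 0.848 - 0.831 = 0.017 at 0.05/3.

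**Step 4: chance imbalance without stratification.** With 22 per arm, 20 percentage points is 4.4 participants, so the event is a difference of 5 or more between the simulator and figurant arms in a given site. Its probability is about 15% with equal sites. With a 50/30/20 split it is about 18%, 14-15% and 9% from the largest to the smallest site. With equal sites, at least one site shows such a difference in about 33% of trials; with site-stratified blocks, practically none do.

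**Step 5: what the imbalance does to the contrast.** For s = 8, the chance shift has SD √(2.614² - 2.422²) = √0.97, or about 1.0 point. As the formula shows, this is a component of the planned analysis's own standard error of 2.61.

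**Step 6: error rate.** In simulations with a site share of 0 to 20% of the variance, the planned analysis had type I error between 0.044 and 0.055.

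**Step 7: if 8.67 is instead the within-site SD.** At site shares of 0, 5, 10 and 20%, simulated power at 0.05 is about 0.89, 0.87, 0.86 and 0.81 as planned. With stratification and a site term it is about 0.89, 0.90, 0.89 and 0.90. At 20%, a site term alone gives about 0.88.

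**The case against.** The strongest reply is that unstratified 1:1:1 randomisation is a valid, openly stated choice. The estimate is unbiased and the test keeps its level (step 6). This stands. A reader might infer that site differences could create a spurious arm difference. They could do so only in the sense of ordinary sampling error, which the planned standard error and the 5% level already cover (step 5).

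Second, the gain rests on an assumed spread. An 8-point span is nearly the whole 8.5-point target difference; at 4 points the gain is 1 to 2 points of power. And if 8.67 is a total SD, the planned analysis keeps about 0.89, close to the intended 90%, so adjustment is a bonus and does not repair a shortfall. This also stands. A loss against the plan appears only on the within-site reading (step 7), which the documents neither state nor exclude.

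Third, it is tempting to add that assessors differ between sites. The documents do not establish this. The outcome description can be read as one instructor, who is also the first author, scoring everywhere. The instructor is singular in the intervention, blinding and limitations text, and the plural under Statistical analyses concerns data registration. The argument from patients and local setting does not need the assessor route, although the documents do not show how far patients differ between the hospitals.

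Fourth, a reader might extend the point to the number of scans at four months. Those scans occur in participants' own departments across four regions, so training centre is only a proxy for workplace, and the planned questionnaire addresses workplace factors more directly. Nothing in the documents supports a claim about that outcome.

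Finally, small blocks within sites make some allocations easier to guess than one trial-wide sequence does. That is a real, if small, cost of stratifying.

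**Conclusion.** The point holds as one of efficiency in the primary analysis. Site appears in neither the allocation nor the model, so whatever between-site variance exists inflates the error of the simulator-figurant contrast. With 8.67 as the total SD and equal sites, a site term gains about 4 points of power at 0.05 for an assumed 8-point span and about 1 point for a 4-point span. If sites hardly differ, the gain is nil and the cost negligible. Visible imbalance of a given site between the two training arms, in about 9-18% of trials, is a matter of presentation and precision. It does not threaten validity. Most of the benefit comes from the site term and little from stratification.

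**What to change.** Prespecify simulation centre as a fixed factor, beside training arm, in the ANOVA of LUS-OSAUS under Statistical analyses and in the primary-outcome row of Table 1. Report the arm contrasts from that model. The cost is two degrees of freedom (63 to 61), and it can be done whether or not allocation has begun, provided it is fixed before the data are unblinded.

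If no participant has yet been allocated, also replace the sentence on site under Randomization with 1:1:1 allocation stratified by site, in permuted blocks of varying size (for example 3 and 6). This needs only a change to the REDCap allocation table, and three strata are not too many for 66 participants. Block sizes should be withheld from site staff, because participants know their arm and short blocks make the sequence more predictable. If that risk is judged to outweigh a gain of at most about 2 points of power, the site term alone is a reasonable choice.

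One added line saying whether 8.67 is a total or within-site SD would show which set of power figures applies.
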